5.1.1 Primary Study Endpoints

Circulating cannabinoid levels

Circulating levels of CBD, Anandamide, Delta-9 THC, 11-Hydroxy Delta-9 THC and Delta-9 Carboxy THC will be assessed in CBD-treated participants 45 minutes after the initial administration (T1, T4), 1 day (T2, T5), 1 week (T3, T6), and 4 weeks (T4, T7) of treatment with each dose of CBD. Anandamide levels will also be assessed at these timepoints in placebo treated participants. Additionally, circulating levels of CBD and anandamide will be assessed in CBD-treated participants 12 hours after ingestion of the preceding evening dose following 1 week (T3, T6) and 4 weeks (T4, T7) of administration of each dose of CBD. Plasma CBD levels will be determined via High Performance Liquid Chromatography/Tandem Mass Spectrometry (LC-MS/MS) by collaborators at the Nathan Kline Institute.

Safety

Safety will be assessed by collection of adverse events at all visits after treatment is initiated. LFTs will be obtained at screening, as well as weeks 4, 8, and 9 to assess liver function during and after treatment with study medication. Risk of suicidality will be assessed using the Columbia-Suicide Severity Rating Scale (C-SSRS) [111] by a licensed Clinical Psychologist, NP or MD as part of each study visit (except for the 1-day/T2 and 4 weeks+1-day/T5 visits).

Psychomotor and subjective effects of CBD:

Basic motoric and cognitive function will be evaluated throughout treatment with several established field sobriety tests, including a walk-and-turn task, one-leg stand, Romberg's test, finger-finger test, and counting backwards [97]. The Addiction Research Center Inventory (ARCI), 49-item version [98], will be used as a measure of the intoxicating effects and abuse potential of CBD. Breath Alcohol Concentration (BAC) will also be measured to ensure participants are not under the influence of alcohol during administration of these tasks. Between-group differences on psychomotor tasks (T1-T8), cognitive measures (T3, T6) and number of adverse events (T1-T9) will be assessed.

Cognitive Function:

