Several established neuropsychiatric and cognitive tasks will be administered to evaluate the impact of CBD vs. placebo treatment on cognitive domains potentially affected by CBD and/or THC. The Rey Auditory Verbal Learning Task (RAVLT) will be used to assess episodic memory [99, 100], the Mental Rotation Task (MRT) will evaluate visuospatial ability [101, 102], a Time Reproduction Task (TRT) will measure encoding and retrieval of time intervals [88], and several WM Span tasks (OSpan, RSpan, SymSpan, RotSpan) will measure working memory capacity [103, 104].

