21.2 Statistical Hypotheses

Hypothesis 1a: Within-group circulating CBD levels will stabilize within one week, i.e. pre-CBD dosing (12 hour) levels obtained after 1 week of treatment will not differ from those obtained after 4 weeks of treatment at each dose.

Hypothesis 1b: Circulating CBD levels obtained at the 1200 mg/day dose will be comparable to those associated with anti-additive effects in animal models, i.e., in the range of 200-400 ng/ml.

Hypothesis 1c: No clinically significant cognitive or motoric impairments, CBD-related serious adverse events, or persisting adverse effects will be observed.

Hypothesis 2a: Relative to placebo, CBD will improve self-report measures of craving, anxiety, mood, and self-efficacy.

Hypothesis 2b: Relative to placebo, CBD will be associated with decreased stress- and alcohol cue-induced craving and physiological stress response

Hypothesis E: Relative to the placebo-treated group, CBD-treated participants will have fewer heavy drinking days during and for four weeks after treatment with 1200mg/day CBD vs. placebo.

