21.3 Description of Statistical Methods

21.3.1 General Approach

The distributional characteristics of the measures used to investigate the aims of the study will be assessed and data transformations will be explored if necessary. For all hypotheses, linear mixed effects models will be constructed including treatment group as a fixed between-subjects factor, time (T0-T9) as a fixed within-subjects factor, and subject as a random effect. Treatment groups will also be compared on baseline measures of alcohol consumption (% drinking days and % heavy drinking days), alcohol craving (PACS), anxiety (BAI), mood (BDI-II), and self-efficacy (AASE), and baseline scores on these measures will be utilized as covariates for hypothesis evaluation.

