21.3.2 Analysis of the Primary Endpoint(s)

For Hypothesis 1a, acute circulating levels of CBD will be assessed in CBD-treated participants 45 minutes after initial administration (T1, T4), and 45 minutes after administration of the morning dose of medication following 1 day (T2, T5), 1 week (T3, T6), and 4 weeks (T4, T7) of treatment with each dose of CBD. Additionally, circulating levels of CBD will be assessed in CBD-treated participants 12 hours after ingestion of the preceding evening dose following 1 week (T3, T6) and 4 weeks (T4, T7) of administration of each dose of CBD. Levels of CBD (mean and standard deviation) will be reported at each timepoint and effects of dose and timepoint will be evaluated. For Hypothesis 1b, circulating CBD levels (mean and standard deviation) 45 minutes after administration of the morning dose of medication following 1 week (T3, T6) and 4 weeks (T4, T7) of treatment with each dose of CBD will be reported in CBD-treated participants. For Hypothesis 1c, between-group differences on psychomotor tasks (T1-T8), cognitive measures (T3, T6) and number of adverse events (T1-T9) will be assessed.

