21.3.6 Baseline Descriptive Statistics

Treatment groups will be compared on several baseline characteristics, including sex, age, race/ethnicity, education level, baseline measures of alcohol consumption (% drinking days and % heavy drinking days), alcohol craving (PACS), anxiety (BAI), mood (BDI-II), and self-efficacy (AASE). Categorical data will be tallied, and means and standard deviations of continuous scores will be calculated.

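### Cognition is part of primary Hypothesis 1c but has no pre-dose score, and the planned covariates omit age and education, so precision is lost and a pre-existing group difference cannot be checked.

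*Combined protocol and SAP*

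**What the plan says.** Cognition is a primary outcome. Hypothesis 1c in section 21.2 reads "No clinically significant cognitive or motoric impairments, CBD-related serious adverse events, or persisting adverse effects will be observed". Section 5.1.1, which lists the primary endpoints, states that "Several established neuropsychiatric and cognitive tasks will be administered to evaluate the impact of CBD vs. placebo treatment on cognitive domains"; the tasks cover episodic memory, visuospatial ability, time reproduction and working memory.

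For the analysis of Hypothesis 1c, section 21.3.2 says that "between-group differences on psychomotor tasks (T1-T8), cognitive measures (T3, T6) and number of adverse events (T1-T9) will be assessed". Sections 5.1.1 and 21.3.2 and the protocol summary all place the cognitive comparison at T3 and T6. In section 8.3, cognitive function appears only in the visit lists for T3 (1 week) and T6 (5 weeks). The screening and T1 lists contain no cognitive task. The columns of the schedule table after section 7.3.2 cannot be read reliably in the available text, and the table shows no separate baseline administration.

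Section 21.3.1 applies to all hypotheses. It specifies a linear mixed model with group, time and a random subject effect, and takes as covariates the "baseline measures of alcohol consumption (% drinking days and % heavy drinking days), alcohol craving (PACS), anxiety (BAI), mood (BDI-II), and self-efficacy (AASE"). Section 21.3.6 adds "sex, age, race/ethnicity, education level" to the baseline characteristics on which the groups are compared, but does not make them covariates. Section 5.1 describes 40 participants randomized 1:1, with no stratification mentioned.

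**The concern.** The plan gives cognition less baseline information than its other outcomes. Craving, anxiety, mood and self-efficacy are analysed from T1, and their baselines are covariates. Psychomotor tasks also start at T1. The cognitive battery has neither its own baseline nor any covariate chosen because it predicts test performance.

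Participants are aged 18 to 65, so two arms of 20 can differ by chance in age, education and prior ability. Without a pre-dose score, nobody can tell afterwards whether a gap at T3 or T6 was already there. Hypothesis 1c predicts no impairment, section 21.3.8 hypothesizes a null difference, and no margin is set. A wide interval that includes zero could therefore be taken as support. An imbalance that hides impairment matters here at least as much as one that mimics it.

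**Working it through.** **Inputs from the documents.** 40 randomized 1:1 (section 5.1), so n = 20 per arm at most; section 7.1.9 limits the primary analyses to participants who complete T7, and no dropout rate is given. Six covariates (section 21.3.1). Alpha 0.05, power 0.95 (section 21.4).

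**Assumptions, not in the documents.** Correlation r between a pre-dose score and the on-treatment score: 0.5 to 0.8. Joint correlation R of age and education with cognition: 0.4 to 0.5. Outcomes are in SD units and tests are two-sided.

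**The plan's own figure.** Section 21.4 says Hypothesis 1c can detect d of about 0.2 at 95% power. For a two-group comparison of 20 per arm (noncentral t, df 38), power at d = 0.2 is 0.09 (0.15 one-sided), and the d detectable at 95% power is 1.17. The stated figure does not reproduce. That is a separate point, but it shows how little precision there is to spare.

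**Step 1, chance imbalance before treatment.** SD of the difference in means = sqrt(2/20) = 0.316. The probability that it reaches 0.3 SD is 34%, and 0.5 SD is 11%.

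**Step 2, what carries into T3 and T6.** Only r times the imbalance carries over, so the shift has SD r × 0.316:

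| r | SD of shift | P(at least 0.3 SD) | P(at least 0.5 SD) |
|---|---|---|---|
| 0.5 | 0.158 | 5.8% | 0.2% |
| 0.6 | 0.190 | 11% | 0.8% |
| 0.7 | 0.221 | 18% | 2.4% |
| 0.8 | 0.253 | 24% | 4.8% |

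**Step 3, 95% half-width at one visit.** With q covariates of joint correlation R, the approximate average half-width is t(38 − q) × sqrt(0.1 × (1 − R²) × (1 + q/(37 − q))); with no covariates the last factor is 1.

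- No covariates: 2.024 × 0.316 = 0.64.
- Six covariates unrelated to cognition (R = 0): 2.037 × sqrt(0.1 × (1 + 6/31)) = 0.70. They need a joint R of about 0.42 to get back to 0.64.
- Age and education as two covariates: R = 0.4 gives 2.028 × sqrt(0.1 × 0.84 × (1 + 2/35)) = 0.60; R = 0.5 gives 0.57.
- Age plus education in four categories (q = 4): 0.62 and 0.59.
- Own-test baseline as one covariate: 0.56, 0.52, 0.46 and 0.39 at r = 0.5, 0.6, 0.7 and 0.8.

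**Step 4, using both visits.** A group effect averaged over T3 and T6 multiplies the half-width by sqrt((1 + ρ)/2), where ρ is the between-visit correlation. With no covariates and ρ assumed 0.5 to 0.8, this gives 0.55 to 0.61 SD. It narrows the interval but removes no pre-existing difference.

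**The case against.** The arms are randomized, so over all randomizations the comparison is unbiased and the type I error is nominal. The 0.316 SD in step 1 is part of the sampling variance already inside the 0.64 SD half-width, so it is not a second source of error. This stands: the loss is in precision and in the ability to check, not in validity.

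A reader might infer that cognition is compared without adjustment. The documents do not support that: section 21.3.1 plans a covariate-adjusted mixed model for every hypothesis. The 0.64 SD figure is a single-visit benchmark, not the planned analysis. The gap is that none of the six covariates is a cognitive score or a demographic predictor. Baseline drinking or mood may predict cognition to some degree; the documents give no figure either way.

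A reader might also take the 34% and 11% as the chance that the on-treatment result is distorted by that much. They describe the pre-treatment difference. The carried-over probabilities are those in step 2.

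Section 5.1.1 says the field sobriety tests cover basic motor and cognitive function, and they start at T1. Section 21.3.4 treats them as a psychomotor battery that is passed or not. They are no baseline for the memory, rotation, timing or span tasks.

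Finally, section 21.1 defers a formal SAP to before database lock and unblinding, so covariates specific to cognition can still be set. That is an opportunity to make the change, not evidence that it is planned.

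**Conclusion.** The point holds in a limited form. A primary safety outcome is measured only on treatment, and the covariates fixed for it omit two predictors that the trial already collects. The gain from using them is modest: about 0.04 to 0.07 SD against no adjustment (0.64 to 0.57–0.60), and about 0.10 to 0.13 SD if the six planned covariates turn out to be unrelated to cognition (0.70 to 0.57–0.60). These sizes rest on the assumed R of 0.4 to 0.5 and on 20 completers per arm; fewer completers would widen every interval.

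A reader might conclude that better covariates, or a baseline battery, would let the trial establish Hypothesis 1c. They would not. With an own-test baseline at r = 0.5 to 0.8, power at d = 0.2 is still only 0.11 to 0.18, and no margin is defined. Nor do the documents support saying that a pre-existing difference will be mistaken for a drug effect. With r = 0.7 and a 0.5 SD imbalance, the conditional false-positive rate is about 10% rather than 5%. The cost of masking is larger: the same imbalance in the hiding direction cuts power for a true 0.8 SD impairment from about 76% (balanced arms) to about 20%.

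**What to change.** **Free, SAP wording only.** Before unblinding, specify age and education level as the covariates for the T3 and T6 cognitive models, in place of reliance on the six drinking, craving, anxiety, mood and self-efficacy covariates. State how education is coded, since four categories cost a few hundredths of an SD in precision. A model with the six covariates of section 21.3.1 can be kept as a sensitivity analysis.

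**Optional, an added assessment.** For participants not yet dosed, give the same battery at T1 before the first dose and use each score as the covariate for its own test. The costs are a longer T1 visit, possible practice effects that need not be equal if the drug affects memory, and partial coverage. Section 6.3 has recruitment running to about August 2021 and the latest logged version is dated July 2021, so few participants may benefit.

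**Reporting, free.** Present the cognitive part of Hypothesis 1c as group differences with 95% confidence intervals, and do not describe a non-significant difference as evidence of no impairment.

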- Is an important medical event that may not result in death, be life-threatening, or require or prolong hospitalization may be considered an SAE when, based upon appropriate medical judgment, the event may jeopardize the subject or may require medical or surgical intervention to prevent one of the outcomes listed above. Examples of important medical events include events requiring intensive treatment in an emergency department, convulsions that do not require in-patient hospitalization, or the development of drug dependency or drug abuse (see Section 8, Other Significant Adverse Events).

***Life-threatening:** Any AE that places the subject, in the view of the investigator, at immediate risk of death from the reaction as it occurred; it does not include a reaction that, had it occurred in a more severe form, might have caused death.

****Disability:** A substantial disruption of a person's ability to conduct normal life functions.

10 Specification of Safety Variables

Safety and toxicity monitoring will be performed throughout the study for all subjects. Safety variables to be assessed include AEs, vital signs, and safety laboratory values, when collected.

The occurrence of an AE or SAE may come to the attention of study personnel during study visits and interviews of a study participant presenting for medical care, or upon review by a study monitor. At each study visit following screening, designated study team members will inquire about the occurrence of AE/SAEs since the last visit.

11 General Guidelines

All AEs, regardless of causality or severity, must be immediately recorded on the AE CRF when volunteered by the subject or solicited through a study assessment questionnaire. The CRC will record all AEs, regardless of causality or severity, with start dates occurring any time after informed consent is obtained until 7 (for AEs) or 30 (for SAEs) days after the last day of study participation on the AE case report forms (CRF). Information to be collected includes event description, time of onset, clinician's assessment of severity, relationship to study product (assessed only by those with the training and authority to make a diagnosis), and time of resolution/stabilization of the event.

Any medical condition that is present at the time that the participant is screened will be considered as baseline and not reported as an AE. However, if the study participant's condition deteriorates at any time during the study, it will be recorded as an AE.

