Changes in the severity of an AE will be documented to allow an assessment of the duration of the event at each level of severity to be performed. AEs characterized as intermittent require documentation of onset and duration of each episode.

At the last scheduled visit, the CRC should instruct each subject to report any subsequent event(s) that the subject, or the subject's personal physician, believes might reasonably be related to participation in this study.

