21.3.4 Safety Analyses

Means and standard deviations of acute circulating CBD and THC levels within CBD-treated participants 45 minutes after initial administration (T1, T4), and 45 minutes after administration of the morning dose of medication following 1 day (T2, T5), 1 week (T3, T6), and 4 weeks (T4, T7) of treatment with each dose of CBD will be assessed to determine whether target circulating levels of CBD have been achieved, and whether metabolic transformation of CBD to THC has occurred.

Means and standard deviations of change in 12 hour circulating CBD levels from 1 week to 4 weeks of treatment (T3 to T4, and T6 to T7) within CBD-treated participants will be presented to determine whether extended treatment with CBD results in accumulation of CBD.

The number of participants within each treatment group that were able to pass a battery of psychomotor field sobriety tasks (walk-and-turn task, one-leg stand, Romberg's test, finger-finger test, and counting backwards [97]) within 2 hours of the initial administration of each dose of CBD vs. placebo (T1 and T4) will be analyzed as summary statistics during treatment.

AEs and SAEs, when present, will be collected on an AE Case Report Form at study visits. The form will include an assessment of clinical significance and study relatedness. Serious Adverse Events (SAEs) will be documented on an additional SAE form. These CRFs will be based on those used in recent NIDA Clinical Trials Network trials. To further assess abuse potential, visual analog scales will be used to assess abuse potential. Scales will include desire to use the study medication again, desire to use the study medication again for pleasurable intoxication ("to get high"), and craving for the study medication.

The study may be stopped if there are untoward and concerning levels of Adverse Event (AE) or Serious Adverse Event (SAE) outcomes attributable to CBD or study participation. If the DSMB finds it is likely that CBD is contributing to negative outcomes, they will consider solutions including protocol changes or potentially stopping the study.

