21.3.9 Tabulation of Individual Response Data

Aside from AEs/SAEs, individual response data will not be presented.

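### The only adverse-event analysis assigned to primary Hypothesis 1c counts events of every kind, so it does not address the related serious events and persisting effects that 1c rules out

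*Combined protocol and SAP*

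**What the plan says.** Section 21.2 words Hypothesis 1c as: "No clinically significant cognitive or motoric impairments, CBD-related serious adverse events, or persisting adverse effects will be observed". The primary objective in section 4.1 makes the same prediction. It has three elements: cognitive or motoric impairment, serious events related to CBD, and adverse effects that persist.

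The analysis assigned to 1c in section 21.3.2 is that "between-group differences on psychomotor tasks (T1-T8), cognitive measures (T3, T6) and number of adverse events (T1-T9) will be assessed". Section 5.1.1 and the protocol summary repeat it almost word for word.

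The count is not restricted in any way, and the recording rule in section 11 is broad: "The CRC will record all AEs, regardless of causality or severity, with start dates occurring any time after informed consent is obtained".

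The information for a narrower analysis is collected. Section 21.3.4 says of the AE form: "The form will include an assessment of clinical significance and study relatedness". Serious events have an additional form. Section 11 also records the "and time of resolution/stabilization of the event". Section 12.3 rates relatedness as probable, possible or unrelated. Section 21.3.9 leaves room for listings: "Aside from AEs/SAEs, individual response data will not be presented".

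Section 21.3.8 describes the primary safety outcomes as ones where no difference between the groups is expected. That is a different statement from no such event being observed.

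**The concern.** Hypothesis and analysis concern different quantities. The hypothesis is about whether particular kinds of event occur at all; the analysis is about whether the arms differ in how many events of any kind are reported. The two can disagree in both directions:

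- CBD may cause more mild, short-lived events. The count then differs between arms, although nothing that 1c rules out has happened.
- A related serious event may occur, or a few events may never resolve. The count is then almost unchanged, although 1c has failed on its own terms.

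What is at stake is the primary safety conclusion. As planned, the reported comparison would not say whether the adverse-event part of 1c held. The two terms needed to judge it are also left open: persisting is not defined, and the three-level relatedness scale is not mapped to CBD-related.

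**Working it through.** **1. Setting the elements of 1c beside the analyses assigned to them**

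| Element of 1c | Analysis in 21.3.2 | Match |
|---|---|---|
| Cognitive or motoric impairment | Psychomotor tasks T1–T8, cognitive measures T3 and T6 | Measures match |
| CBD-related serious events | Number of adverse events T1–T9 | No restriction to serious or related |
| Persisting effects | Number of adverse events T1–T9 | No use of resolution |

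**2. The plan's own figure.** The only number tied to 1c is in section 21.4: a detectable effect of about d = 0.2 at power 0.95 and alpha 0.05 with 40 participants. A single between-group comparison with 20 per arm does not reproduce it: power at d = 0.2 is about 9% two-sided, and 95% power needs d of about 1.17. That is a separate matter, and nothing below depends on it.

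**3. A forbidden event occurs and the count is silent.** Inputs: 20 per arm (40 randomised 1:1, section 5.1); event numbers assumed.
- 40 non-serious events in each arm plus one related serious event on CBD gives 41 vs 40. The exact binomial test of 41 out of 81 against one half gives p = 1.0.
- With equal event rates plus two related serious events on CBD, the simulated chance of a significant difference is about 5%, which is the test's own type I error.

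**4. No forbidden event occurs and the count differs.** Assumptions, since the documents give no rates: placebo mean 1, 2 or 4 events per participant; Poisson counts, or negative binomial counts with dispersion k = 2 or 1; every event non-serious and transient. The test is a two-sided t-test at 0.05 on per-participant totals, a simplification of the mixed model in section 21.3.1, with 20,000 simulated trials per cell. Entries are the percentage of trials with a significant difference, for placebo means 1 / 2 / 4.

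| Rate ratio | Poisson | k = 2 | k = 1 |
|---|---|---|---|
| 1.25 | 11 / 18 / 30 | 8 / 10 / 12 | 7 / 8 / 9 |
| 1.5 | 28 / 49 / 79 | 18 / 24 / 30 | 14 / 16 / 19 |
| 2.0 | 72 / 95 / 100 | 46 / 61 / 71 | 33 / 40 / 45 |

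Section 3.4.1 lists diarrhoea, somnolence, decreased appetite and fatigue among the events commonly reported in Phase 3 trials of CBD for seizure disorders. A rate ratio above 1 is therefore conceivable, but the documents do not give its size.

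**5. What a matched summary could show.**
- If 0 of 20 CBD participants have a related serious event, the one-sided 95% upper limit is 1 − 0.05^(1/20) = 13.9% (two-sided exact limit 16.8%).
- If the true risk is 1%, 5% or 10%, the chance of seeing at least one event in 20 is 1 − 0.99^20 = 18%, 1 − 0.95^20 = 64% or 1 − 0.90^20 = 88%.
- A test between arms would add little: Fisher's exact p is 0.106 for 4 vs 0 and first falls below 0.05 at 5 vs 0 (p = 0.047).

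**The case against.** Several points on the other side are fair.

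- *A related serious event would be seen.* This stands. Such events have their own form, relatedness is recorded, and AE/SAE data are exempt from the rule against individual presentation. A reader might infer that 1c would be declared intact despite such an event. The documents do not support that: one related serious event contradicts 1c on inspection, and nothing says 1c is decided by the significance of the count. What remains is that the assigned analysis does not address the question, and a listing neither defines persistence nor says which ratings count as related.
- *Relatedness and duration are used elsewhere.* Also true. Section 18 triggers a DSMB review after three severe, probably related events, the DSMB receives an aggregate analysis (sections 19 and 21.3.7), and section 11 foresees assessing event duration at each severity level. So it would be wrong to say these data are never used. None of these uses is a planned summary for 1c.
- *One participant could drive the count.* A reader might infer this from section 11: "AEs characterized as intermittent require documentation of onset and duration of each episode". That sentence concerns documentation and does not make each episode a separate event. Section 12.2 defines a mild event as one with multiple occurrences, and the model in section 21.3.1 has subject as a random effect. The inference is not shown.
- *Visits T8 and T9 fall after dosing ends.* A by-visit count there carries some information on effects that outlast treatment. It is imperfect, because the plan does not say whether a visit's count is of new or ongoing events.
- *A formal SAP is still to come* (section 21.1). This makes the gap easy to close, but section 21.3.2 already commits to the mismatched measure.

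**Conclusion.** The concern holds for the adverse-event part of 1c only. It rests on the wording of sections 4.1, 21.2 and 21.3.2 and needs no assumption. A reader might infer that 1c as a whole is untested; that goes too far, because matching measures are named for its cognitive and motoric element.

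How often the count would mislead cannot be fixed from the documents. Under the assumed rates, a significant difference made up entirely of non-serious, transient events arises in about 7–30% of trials at a rate ratio of 1.25, 14–79% at 1.5 and 33–100% at 2.0. The high figures need a doubling of the event rate and should not be quoted alone. In the other direction, one or two related serious events leave the count comparison essentially where it was. The change is worth making because it concerns a primary safety conclusion and costs little.

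**What to change.** In section 21.3.2, for the adverse-event element of 1c only, replace the event-count comparison with two participant-level summaries by arm, each with exact confidence intervals:

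1. Participants with at least one serious adverse event rated possibly or probably related.
2. Participants with at least one adverse event that began between first and last dose and is unresolved at the last contact up to T9. Show this overall and restricted to events rated possibly or probably related, and report participants not reached at T9 separately.

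The onset window and the related-only version keep a late, unrelated illness from counting as persisting. Assess this element of 1c on these two summaries, leave the cognitive and motoric analyses as they are, and keep the total event count as supportive. State the denominator as well: section 7.1.9 limits the primary analyses to those who complete treatment through T7, so a participant who left early with a related serious event could otherwise drop out of the table.

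The cost is SAP wording and two tables from data already collected, settled before unblinding. The downside is that these events will be rare, so the result is mainly descriptive: 0 of 20 on CBD still leaves a one-sided 95% upper limit of about 14%.
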